22. Known to be human immunodeficiency virus (HIV) positive
23. Active viral hepatitis (B or C) as demonstrated by positive serology at Screening
24. Psychotic disorder(s) or unstable recurrent affective disorder(s) evident by use of antipsychotics or prior suicide attempt(s) within approximately the last 2 years
25. History of drug or alcohol dependency or abuse within approximately the last 2 years; use of illegal recreational drugs
26. Concomitant use of medications known to be inducers of cytochrome P450 (CYP3A) including, but not limited to: rifampin, troglitazone, St John's Wort, efavirenz, nevirapine, glucocorticoids (other than topical usage), modafinil, pioglitazone, and rifabutin.
27. Use of AEDs not recommended by Epilepsy Treatment Guidelines for use in LGS including, but not limited to carbamazepine, gabapentin, oxcarbazepine, phenytoin, pregabalin, tiagabine, and vigabatrin (revised per Amendment 02)
28. Any suicidal ideation with intent with or without a plan within 6 months before Visit 2 (ie, answering "Yes" to questions 4 or 5 on the Suicidal Ideation section of the C-SSRS) in subjects aged 8 and above. (revised per Amendment 01)
29. Subjects with rare hereditary problems of galactose intolerance, the Lapp lactase deficiency or glucose-galactose malabsorption. (revised per Amendment 04)

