5.6.2 Adverse Events

The AE verbatim descriptions (investigator terms from the CRF) will be classified into standardized medical terminology using the Medical Dictionary for Regulatory Activities (MedDRA). Adverse events will be coded to the MedDRA (Version 24.1 or higher) lower level term (LLT) closest to the verbatim term. The linked MedDRA preferred term (PT) and primary system organ class (SOC) will also be captured in the database.

A TEAE is defined as an AE that emerged during treatment, having been absent at pre-treatment (Baseline) or

- Re-emerged during treatment, having been present at pre-treatment (Baseline) but stopped before treatment, or
- Worsened in severity during treatment relative to the pre-treatment state, when the AE was continuous.

Only those AEs that are treatment emergent will be included in summary tables. All AEs, treatment emergent or otherwise, will be presented in subject data listings.

TEAEs will be summarized by treatment group and by age group. The incidence of TEAEs will be reported as the number (percentage) of subjects with TEAEs by SOC and PT. A subject will be counted only once within a SOC and PT, even if the subject experienced more than one TEAE within a specific SOC and PT. The number (percentage) of subjects with TEAEs will also be summarized by maximum severity (mild, moderate, or severe).

The number (percentage) of subjects with TEAEs will also be summarized by relationship to study drug (related and not related). Summaries of treatment-related TEAEs will be produced.

There will also be summaries of TEAEs by dose at onset and exposure-adjusted event rates.

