5.6.6 Other Safety Analyses

5.6.6.1 C-SSRS

Scoring of the C-SSRS will be performed as suggested by the C-SSRS Columbia website http://www.cssrs.columbia.edu/clinical_trials.html.

The following summaries will be presented for the treatment duration (defined as the period from the date of first dose up to 28 days after the date of last dose, inclusive).

- Number (percentage) of subjects with any treatment-emergent report of suicidal behavior, suicidal ideation, and suicidality (suicidal behavior and/or ideation) will be displayed. A treatment-emergent report of suicidal behavior, suicidal ideation, or suicidality is an answer of 'Yes' to any question in the respective category during the treatment duration.
- Shift from baseline to the maximum suicidal ideation severity rating (0=no ideation present to 5=active ideation with plan and intent) in the treatment duration will assess worsening of suicidal ideation. Any score greater than 0 indicates the presence of suicidal ideation while a score of 4 (active suicidal ideation with some intent to act) or 5 (active suicidal ideation with specific plan and intent) can be used to indicate serious suicidal ideation.

Descriptive statistics and changes from baseline will be presented by visit for the suicidal ideation severity rating (treated as a continuous variable) to assess change in suicidal ideation over time.
Other Analyses

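### The C-SSRS count labelled treatment-emergent has no baseline condition, so ideation that merely persists is counted as emergent

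*SAP*

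**What the plan says.** Core SAP 5.6.6.1 plans the number and percentage of subjects with treatment-emergent suicidal behaviour, suicidal ideation, and either of the two combined. Its definition begins "A treatment-emergent report of suicidal behavior, suicidal ideation, or suicidality is an answer of"; the required answer is Yes. That answer may be given, in the SAP's words, "to any question in the respective category during the treatment duration". The treatment duration is "defined as the period from the date of first dose up to 28 days after the date of last dose, inclusive". The rule contains no baseline condition.

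The same section plans two summaries that do use baseline, both for ideation severity only: "Shift from baseline to the maximum suicidal ideation severity rating" and "Descriptive statistics and changes from baseline will be presented by visit for the suicidal ideation severity rating".

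Extension SAP 5.5.6.1 repeats the definition in the same words. It plans no other C-SSRS summary.

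For adverse events, Core SAP 5.6.2 gives the term a different meaning. "A TEAE is defined as an AE that emerged during treatment, having been absent at pre-treatment (Baseline) or" begins the definition. The alternatives are re-emergence after having stopped before treatment, and "Worsened in severity during treatment relative to the pre-treatment state, when the AE was continuous". Extension SAP 5.5.2 uses the same three limbs.

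On eligibility, criterion 28 in Protocol 9.3.2 excludes "Any suicidal ideation with intent with or without a plan within 6 months before Visit 2", which it ties to a Yes on question 4 or 5 in subjects aged 8 and above.

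**The concern.** One word carries two meanings in one safety report. In the adverse event tables, treatment-emergent means something changed relative to the pre-treatment state. In the C-SSRS table it means only that a Yes was recorded after first dose. A reader who carries the first meaning into the second table will take persisting ideation for new ideation.

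The trial can enrol the subjects for whom this matters, because criterion 28 leaves ideation at questions 1 to 3 eligible. Such a subject who answers Yes again on treatment enters the ideation row and the combined suicidality row, even if the severity rating fell.

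Suicidality is monitored throughout the study, and the protocol has subjects judged at high risk withdrawn, so the headline C-SSRS count will be read closely. In the Extension every subject is on perampanel, so there is no concurrent control rate against which to judge an inflated count.

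**Working it through.** No C-SSRS rate, sample size or test in the documents depends on this definition, so there is no stated figure to reproduce. The check is a comparison of rules, then an illustration.

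**Rules side by side (Core SAP)**

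| Measure | Section | Baseline condition |
|---|---|---|
| Treatment-emergent adverse event | 5.6.2 | Absent before, re-emerged, or worsened |
| Treatment-emergent markedly abnormal laboratory value | 5.6.3 | Grade must rise from baseline |
| Clinically notable vital sign | 5.6.4 | Change from baseline also required |
| Treatment-emergent C-SSRS report | 5.6.6.1 | None |

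Section 8.2.1 defines a baseline for every safety endpoint, and Protocol Table 5 schedules a C-SSRS before first dose. The data for a baseline-referenced count therefore exist.

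**Test case.** A subject has an ideation rating of 3 at baseline and a maximum of 1 on treatment. Criterion 28 does not exclude the subject. The shift table shows improvement, while the headline row counts a treatment-emergent report.

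**Ceiling on the number miscounted.** Take 71 subjects per arm (SAP section 4) and an assumed share b with ideation at baseline, all of whom answer Yes again without worsening:

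- b = 1%: 71 × 0.01 = 0.7, about 1
- b = 5%: 71 × 0.05 = 3.6, about 4
- b = 10%: 71 × 0.10 = 7.1, about 7

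These are upper bounds. The trial enrols from age 2, but Protocol 9.5.1.5 gives the C-SSRS only to subjects aged 8 or over at consent or reaching 8 during the double-blind phase, so fewer than 71 per arm may be assessed. Not every subject with baseline ideation will answer Yes again, and some who do will have worsened and belong in the count.

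**Effect on the comparison of arms.** Let s be the share of baseline-positive subjects who answer Yes again, and e the rate of new ideation among the rest. For simplicity, assume no baseline-positive subject worsens.

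- SAP count: b·s + (1 − b)·e
- Baseline-referenced count: (1 − b)·e

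With assumed e = 1% on placebo and 3% on perampanel, and equal b and s in both arms:

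| b | s | SAP count, placebo vs perampanel | Baseline-referenced count | SAP ratio | Referenced ratio | Difference, both counts |
|---|---|---|---|---|---|---|
| 0% | any | 1.00% vs 3.00% | 1.00% vs 3.00% | 3.0 | 3.0 | 2.00 points |
| 2% | 50% | 1.98% vs 3.94% | 0.98% vs 2.94% | 2.0 | 3.0 | 1.96 points |
| 5% | 100% | 5.95% vs 7.85% | 0.95% vs 2.85% | 1.3 | 3.0 | 1.90 points |
| 10% | 100% | 10.90% vs 12.70% | 0.90% vs 2.70% | 1.2 | 3.0 | 1.80 points |

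The term b·s raises both rates and pulls their ratio toward 1. It cancels from the difference, which stays close to the 2.00 points seen when b = 0.

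**The case against.** The strongest reply is that the SAP defines its term explicitly, so the row is reproducible, and that it errs toward over-counting, the safer direction for suicidality. Both statements are true. They argue for keeping the count, not for its label.

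Several stronger readings are tempting, and the documents do not support them:

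- **That the C-SSRS is never compared with baseline.** In the Core Study, stable ideation falls on the diagonal of the planned shift table, and by-visit change is planned too. SAP 5.6.2.2 also plans a listing and summary of suicidality adverse events, and 5.6.2 restricts summary tables to treatment-emergent events. For Core ideation the fault is confined to the headline count and its label.
- **That the rule masks a treatment difference.** The working shows the difference is almost unchanged. SAP 5.6 treats safety descriptively, and no C-SSRS test or ratio is planned.
- **That the Extension SAP attributes persisting ideation to perampanel.** Treatment-emergent is a timing label, and the plan makes no causal claim. Extension SAP section 7 also says its summaries are limited because the study terminated early, so the shorter C-SSRS output is a declared reduction.
- **That behaviour already reported at baseline should not count.** Behaviour repeated on treatment would qualify under the SAP's own re-emergence limb. Dropping it would remove real on-treatment events.

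SAP 5.6.6.1 refers scoring to an external website. Whether the counting rule follows that source cannot be checked from the documents, but the conflict with the SAP's own terminology does not depend on it.

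Part of the concern survives these points. The combined suicidality row has no baseline-referenced C-SSRS summary in either SAP. In the Extension the count stands alone, and the standardized query list in Extension SAP 5.5.2.1 contains no suicide or self-injury query.

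**Conclusion.** The point holds as a labelling and definition fault in a safety summary. Both SAPs call any on-treatment Yes treatment-emergent, so unchanged or improved ideation at questions 1 to 3 is counted as emergent in the ideation and combined rows. Core ideation can be untangled from the other planned tables. Core combined suicidality and the Extension cannot be untangled from the C-SSRS summaries planned.

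The size cannot be established, because the documents give neither baseline prevalence nor the number of subjects assessed. It is zero if no subject has baseline ideation. The figures of 1, 4 and 7 per arm should not be read as estimates: they are ceilings at assumed prevalences of 1%, 5% and 10%. The statement that rates rise, the ratio shrinks and the difference barely moves assumes equal baseline prevalence and persistence in the two arms. No primary or key secondary result is affected. The change is worth making because it is cheap, not because a conclusion of the trial turns on it.

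**What to change.** In both SAPs:

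1. Relabel the present row as any on-treatment report. Extension SAP 5.5 already describes the measure as on-treatment suicidality.
2. Add a treatment-emergent row that counts:
   - (a) a maximum on-treatment ideation rating above the baseline rating, or ideation that had stopped before treatment and returned; and
   - (b) any suicidal behaviour occurring on treatment, including repeat behaviour in subjects with earlier behaviour.
3. Derive combined suicidality as (a) or (b).

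In the Extension SAP, add the shift from baseline to maximum ideation rating, using the baseline in its section 8.2.1 (last value before first perampanel dose).

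The cost is one sentence in each SAP, one extra table row and one Extension table. All of it uses C-SSRS data already collected, and the existing count is kept.

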5.7 OTHER ANALYSES

5.7.1

CCI

CCI

CCI

5.7.2

CCI

CCI

5.7.3

CCI

CCI

CCI

5.7.4

CCI

CCI

5.8 EXPLORATORY ANALYSES

CCI

5.9 EXTENSION PHASE ANALYSES

The statistical methods used in the extension phase will be described in a separate SAP.

6 INTERIM ANALYSES

No interim analyses are planned for this study.

7 CHANGES IN THE PLANNED ANALYSES

There are no changes to the statistical methods in this analysis plan compared to the protocol. Any future changes to the analysis will be documented separately and will be addressed in the Clinical Study Report.

8 DEFINITIONS AND CONVENTIONS FOR DATA HANDLING

8.1 EFFICACY DATA HANDLING

Only “valid days” and “valid seizure counts” will be used in the calculations of seizure frequency per 28 days. A “valid day” is defined as the day where seizure counts information is present, that is, either a record with an answer of ‘No’ to the question ‘Did the subject experience any seizures?’ or a positive number of seizures for at least one of the seizure types collected. “Valid seizure counts” are the seizure counts that are read from the valid seizure days.

8.1.1 Pre-randomization/Baseline Efficacy

All diary data prior to first dose date will be used in the computation of Prerandomization Phase seizure frequency per 28 days. All subjects should have approximately 4 weeks of diary data prior

to baseline (Visit 2). The baseline value for other efficacy endpoints will be the last non-missing measurement occurring prior to the first dose of the study drug.

8.1.2 Treatment Duration for Efficacy Analyses

The date of first dose of the study drug is considered Day 1 in the treatment duration.

The first dose date is the study drug start date and the last dose date is study drug end date from the study medication CRF page.

The treatment duration for efficacy variables is defined as follows:

- For diary seizure data: The duration between the day of first double-blind study drug dose and the last day of double-blind study drug dose, inclusive.
- For non-diary efficacy data: The duration between the day of first double-blind study drug dose and 7 days after the last double-blind study drug dose, inclusive.

For all efficacy analyses, data reported only during the treatment duration will be analyzed.

8.1.3 Handling of Replicate Data

If there is more than 1 diary entry for a date, then the entry with the highest number of drop seizures will be used for that date.

For the CGIC assessment, the last visit, within the treatment duration will be used.

8.2 SAFETY DATA HANDLING

8.2.1 Baseline safety

The baseline value for all safety endpoints will be the last non-missing measurement occurring prior to the first dose of the study medication.

8.2.2 Treatment Duration for Safety Analyses

The treatment duration for non-AE safety variables is considered to begin at or after the first dose of study drug on Day 1 and ends 14 days after the last dose of double-blind study medication. For AEs, the treatment duration is considered to begin on Day 1 and ends 28 days after the last dose of double-blind study medication.

The post-treatment duration is considered to begin on the day after the treatment duration for safety. Since it is not always possible for all study participants to come in for their clinic visits on the exact day specified in the protocol schedule, the visit week of a subject's visit will be based on the actual visit occurring during the treatment duration. These visits will be used to create by visit summaries for laboratory, and vital signs data. The end of treatment value is the last non-missing value in the treatment duration.

Any concomitant medication taken within the 14 days after the last dose data will be listed/summarized as part of the concomitant medication listing/table.

AEs for the subject were collected and reported on CRF starting from the time the subject signed informed consent to the last visit in the Treatment Phase following the subject's last dose. Serious AEs were collected for 28 days after the last dose.

For summaries of safety by time points, the time points will be relative to date of first dose. For standardized reporting, study day windows relative to the first dose (Day 1) in the study will be applied to determine into which week the data will be mapped. Scheduled, unscheduled, and early withdrawal visits will be mapped to weeks. [Table 2](#) below gives the mapping of relative day ranges to week for vital sign assessments. [Table 3](#) below gives the mapping of relative day ranges to week for laboratory assessments. If a subject did not have a recorded observation falling within a given range of days in order to be assigned to a week, the subject's data for that week will be regarded as missing for summarization purposes. If there are two or more assessments in the same window then:

- if the window is the baseline assessment, then the latest assessment will be used in the summary tables;
- if the window is the follow-up assessment, then the latest assessment will be used in the summary tables;

If the window is not the baseline or the follow-up assessment, then the assessment closest to the scheduled assessment will be used in the summary tables. Note that if two assessments are equidistant from the scheduled assessment then the earliest assessment of the two (within the allowable window) will be used. .

Table 1: Mapping of Study Day Ranges to Week for Vital Signs and Weight

Windowing Period	Study Day Range (Relative to First Dose)	Week
Pretreatment	Day $\leq 1^a$	0
Treatment	$2 \leq \text{Day} \leq 20$	2
Treatment	$21 \leq \text{Day} \leq 31$	4
Treatment	$32 \leq \text{Day} \leq 66$	7
Treatment	$67 \leq \text{Day} \leq 104$	12
Treatment	$105 \leq \text{Day} \leq 140$	18
	Day Relative to 14 Days After Last Dose	
Post-Treatment	Day $\leq 999^c$	4

- a: All assessments performed on the same date as the date of first dose were to be performed prior to dosing; results from these assessments will be regarded as Pretreatment values in the analyses.
- b: Measurements must have been taken during the treatment duration, ie, within 14 days of the day of last dose, to be included in analyses as on-treatment assessments.
- c: Measurements must have been taken more than 14 days after the day of last dose to be included in analyses as Post-treatment assessments. Target day is 28 days after last dose or Post-treatment Week 4.

It should be noted that for the post-treatment duration, the study week window is defined relative to the last dose, rather than to the first dose.

Table 3: Mapping of Study Day Ranges to Week for Laboratory Assessments

Windowing Period	Study Day Range (Relative to First Dose)	Week
Pretreatment	Day $\leq 1^a$	0
Treatment	$2 \leq \text{Day} \leq 76$	4
Treatment	$77 \leq \text{Day} \leq 140$	18
	Day Relative to 14 Days After Last Dose	
Post-Treatment	Day $\leq 999^c$	4

- a: All assessments performed on the same date as the date of first dose were to be performed prior to dosing; results from these assessments will be regarded as Pretreatment values in the analyses.
- b: Measurements must have been taken during the treatment duration, ie, within 14 days of the day of last dose, to be included in analyses as on-treatment assessments.
- c: Measurements must have been taken more than 14 days after the day of last dose to be included in analyses as Post-treatment assessments. Target day is 28 days after last dose or Post-treatment Week 4.

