9.3.3 Removal of Subjects from Therapy or Assessment

The investigator may withdraw the subject from the study at any time for safety or administrative reasons. The subject may stop study drug or withdraw from the study at any time for any reason.

Subjects with laboratory results that include elevated AST or ALT greater than or equal to $3 \times$ ULN and elevated total bilirubin (TBIL) greater than or equal to $2 \times$ ULN with an alkaline phosphatase (ALP) laboratory value that is less than $2 \times$ ULN, ie that meet criteria for Hy's law, will be withdrawn from the study. (revised per Amendment 03) Subjects who appear to have a high risk of suicidal behavior according to results of the C-SSRS and/or clinical impression will be withdrawn from the study. (revised per Amendment 03)

A subject who discontinues study treatment should be followed for subsequent protocol-specified visits and procedures. If a subject discontinues study drug(s) but remains in the study (Core Study), the set of end-of-treatment procedures will be administered, and protocol-specified information will be collected. The primary reason for discontinuation and all other reason(s) contributing to the subject's discontinuation from study drug(s) should be collected on the Subject Disposition case report form (CRF) page (or the Early Discontinuation from Study Drug CRF page). In addition, the date of last dose of study drug(s) will be recorded on the Study Drug Dosing CRF page. If a subject discontinues study treatment and the study at the same time, the End-of-Study procedures (Final Visit) will be followed.

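### SAP 8.2.2 can report a vital-sign or laboratory value taken long after the last dose as Post-Treatment Week 4, because it keeps the latest value in an effectively open-ended window

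*SAP*

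**What the plan says.** SAP 8.2.2 has one window table for vital signs and weight and another for laboratory tests. Each has a single post-treatment row, with Day 999 as its upper limit and Week 4 as its label. Footnote c sets the lower limit: "Measurements must have been taken more than 14 days after the day of last dose to be included in analyses as Post-treatment assessments". It also names the target: "Target day is 28 days after last dose or Post-treatment Week 4".

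When several values fall in that row, the text says "if the window is the follow-up assessment, then the latest assessment will be used in the summary tables". For windows other than baseline and follow-up the rule differs: "then the assessment closest to the scheduled assessment will be used in the summary tables". The mapping is not confined to planned visits: "Scheduled, unscheduled, and early withdrawal visits will be mapped to weeks".

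The anchor is stated in two ways. The column header reads "Day Relative to 14 Days After Last Dose", while the note under the first table says that for the post-treatment period "the study week window is defined relative to the last dose, rather than to the first dose".

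Protocol 9.3.3 states: "A subject who discontinues study treatment should be followed for subsequent protocol-specified visits and procedures". The sentence after it deals with a subject who stops drug but stays in the Core Study.

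**The concern.** A 28-day target has no effect when the selection rule ignores it and the window has no practical end. A subject who stops drug early and keeps attending can have several values in the row, and the rule picks the one furthest from the target. SAP 5.6.3 and 5.6.4 call for summaries at each post-baseline visit, so a reader of the Week 4 row would take it as status about four weeks off drug. For some subjects it could be status ten or more weeks off drug, with a better-timed value left out.

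**Working it through.** **Inputs.** Protocol Table 5 schedules vital signs on Days 8, 22, 43, 85 and 127 (Visits 3 to 7) and laboratory tests on Days 22 and 127. Both are also done at the 4-week follow-up visit. Follow-up visits have a ±6-day window (Table 5, footnote e). The last-dose days below are assumptions; the documents give no distribution of stopping times.

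**The plan's own target.** The 4-week follow-up is on Day 155 and Visit 7 is on Day 127. 155 − 127 = 28 days, which agrees with footnote c.

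**Upper limit as written.** If anchored on the last dose: 999 days, or 999 / 7 = about 143 weeks. If anchored 14 days later, as in the header: 999 + 14 = 1013 days, or 1013 / 7 = about 145 weeks.

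**Value selected for an off-drug attender.** Let L be the day of the last dose. Visit 7 falls 127 − L days later and enters the row if that exceeds 14.

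| L (assumed) | Visit 7, days after last dose | Kept by the latest rule | Closest to 28, if a 4-week visit was held |
|---|---|---|---|
| 22 | 105 | 105 | 28 |
| 30 | 97 | 97 | 28 |
| 43 | 84 | 84 | 28 |
| 57 | 70 | 70 | 28 |
| 85 | 42 | 42 | 28 |
| 99 | 28 | 28 | 28 |

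For L = 30, Visit 5 (Day 43, +13) is still on treatment. Visit 6 (Day 85, +55, vital signs only) and Visit 7 (+97) both enter the row, and +97 is reported. That is 97 − 28 = 69 days past the target.

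For L = 57, a well-timed vital-sign value exists even without a separate follow-up visit: Visit 6 is at 85 − 57 = 28 days. The rule still reports Visit 7 at 70 days.

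**Where the effect stops.** Visit 7 comes after a 4-week follow-up visit only if 127 > L + 28, that is, L < 99. For L from 100 to 112 the follow-up visit is the later one, so the latest rule keeps the 28-day value. From L = 113, Visit 7 is at most 14 days after the last dose and is not post-treatment. Visit windows make these limits approximate.

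**Subjects with no later scheduled visit.** For a subject who completes treatment without rolling over, or who leaves the study, the 4-week visit is the only scheduled value in the row. The 1-week follow-up has neither assessment and, at 7 + 6 = 13 days at the latest, falls inside the 14-day limit. Only a later unscheduled visit could change the result.

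**The case against.** Day 999 is probably a programmer's open-end marker, and for most subjects the row holds a single value near 28 days. That is fair. But no other limit is written, and an open end becomes a problem when combined with keeping the latest value.

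It is also not clear that an off-drug attender has a separate 4-week follow-up visit. Protocol 9.1.2.3 and Table 5 footnote e tie that visit to subjects who do not enter Extension A or who leave the study, whereas 9.3.3 sends subjects who stay to the later scheduled visits. This stands: the loss of a 28-day value in the Day 30 example is conditional. Without that visit the Day 127 value is still labelled Week 4.

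The reach is small. Under SAP 5.6.3, markedly abnormal laboratory values are counted over all scheduled and unscheduled visits. Maximum liver values and end-of-treatment values come from the treatment period. None of these depends on the rule.

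A reader might infer that Extension A visits of every roll-over subject also fall in the row, since footnote c sets only a minimum time since the last dose. The documents do not support that. SAP section 3 limits the plan to the Core Study and section 5.9 sends the extension to a separate SAP. Protocol Table 5 footnote e says the Core follow-up visits are not held for subjects who continue. The extension SAP (5.5.3 and 5.5.4) only lists laboratory and vital-sign data.

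**Conclusion.** The point holds as a minor one. The selection rule and the open window conflict with the SAP's own 28-day target and can put a value taken 42 to 105 days after the last dose (assumed stops from Day 85 back to Day 22) under a Week 4 label. Through scheduled visits this needs a subject who stops before about Day 99 and keeps attending; otherwise it needs a late unscheduled visit. The number of such subjects is not given, so the effect on the summary cannot be sized. Two broader statements go too far: that every subject who stops drug is affected, and that the row is designed to show recovery or withdrawal, a purpose the SAP does not state. The consequence is confined to the post-treatment row of the by-visit descriptive summaries.

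**What to change.** In SAP 8.2.2:

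- Change the follow-up bullet to keep the assessment closest to 28 days after the last Core dose. This returns the 28-day value in every case tabulated above in which a 4-week visit is held.
- Bound the post-treatment row in both tables. One choice is 15 to 42 days: 28 ± 14, with the lower end set by the existing rule of more than 14 days. It contains the protocol's visit window of 28 ± 6, that is, 22 to 34 days. The exact bound is a matter of preference, but some bound is needed for subjects with no 4-week visit.
- List later off-drug values separately.
- Reconcile the header with the note, and state that days count from the last dose. Otherwise a row of 15 to 42 under the present header would mean 15 + 14 = 29 to 42 + 14 = 56 days after the last dose and would miss the target.

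This changes one bullet, one row in each table and the header wording. The cost is that a few late values move from the summary to a listing.
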